### **10.3.2 Data Collection and Follow-up for Withdrawn Subjects**

Subjects who withdraw consent and refuse to complete the follow-up assessment, fail to adhere to protocol requirements, or die during the follow-up phase will be considered off-study at that time. Attempts will be made to retrieve any follow-up data, in particular, regarding possible AEs at the time of study discontinuation. If the Investigator(s) reports a subject as lost to follow-up, the Clinical Research Associate (CRA) will ensure that documentation is made regarding the reason(s) this has occurred and will ensure that every attempt is made by the Investigator(s) to contact the subject to determine subject status. Appropriate documentation will consist of at least two documented attempts at contact via telephone, followed by an attempt to contact via a registered US/Canada post letter.

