## 8. STUDY ENDPOINTS

### 8.1 Primary Endpoint

The primary endpoint is to evaluate the change in Knee and Osteoarthritis Outcomes Scores (KOOS) scores at Week 52 post-operative compared to baseline.

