## **10.3 Early Withdrawal of Subjects**

### **10.3.1 When and How to Withdraw Subjects**

Subjects may voluntarily withdraw from the study at any time for any reason. The Investigator(s) may elect at any time to withdraw a subject from the study for any reason unrelated to the study if such a decision is in the subject's best medical interest. Subjects who experience an AE may also voluntarily withdraw or be withdrawn if deemed in the subject's best medical interest. If a subject discontinues the study prematurely or is withdrawn by the Investigator(s), data collected up to the time of withdrawal will be used

if applicable for analysis. The primary reason for termination or discontinuation will be documented on the End of Study CRF. Subjects who are withdrawn for any reason from the study after intervention will not be replaced.

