### **12.3 Sample Size Determination, Power calculation, and Rationale**

[figure not shown]
This study will be conducted in a two parts. There is no power calculation for the Part I study. In the Part II study subjects will be randomized to one of the two treatment groups in a 1:1 ratio.

A total of 82 subjects (41 in the study device group and 41 in the control device group) will be randomized in an effort to assure that seventy (70) subjects (i.e., 35 subjects per group) complete the study.

PASS version 2011, is used for this sample size and power calculation. The requirement of 70 subjects (35 active and 35 control) is based on achieving 80% statistical power to detect a non-inferiority margin difference of 8 points between the two groups (10). For the same 80% statistical power, and significance level (alpha) of 0.05 two-sided test; one may choose different number of subjects depending on the expected and observed KOOS score and the acceptance of the non-inferiority delta. These are depicted in Figure 12-1 below.

The discontinuation rate is predicted to be no more than 15%. To accommodate the potential discontinuations, 82 randomized subjects (41 in the study device group and 41 in the control device) are needed for this study.

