## **12.6 Analysis Populations**

### **12.6.1 Intent-to-Treat Population**

The Intent-to-Treat (ITT) population is defined as all randomized subjects. The Intent-to-Treat population will be the primary population for the analysis of the primary and secondary endpoints.

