### **12.7.5 Efficacy Analyses**

#### ***12.7.5.1 Primary Analysis***

##### Primary Endpoint:

The primary analysis will be conducted on the Intent-to-treat (ITT) population. The change in Knee and Osteoarthritis Outcomes Scores (KOOS) from baseline will be compared between the device/treatment groups using Repeated Measures Analysis of Covariance.

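### Protocol section 10.3.2 makes undefined non-adherence a stand-alone ground for off-study status, which can end Week 52 KOOS collection in consenting randomised subjects

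*Protocol*

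**What the plan says.** Section 10.3.2 names three kinds of subject: those who withdraw consent and also refuse the follow-up assessment, those who do not adhere, and those who die. For the last two its words are "fail to adhere to protocol requirements, or die during the follow-up phase will be considered off-study at that time". What follows off-study status is an effort at retrieval: "Attempts will be made to retrieve any follow-up data, in particular, regarding possible AEs at the time of study discontinuation".

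Section 10.3.1 sets out when subjects are withdrawn, either by their own choice or by the investigator in their best medical interest. It does not mention non-adherence. For those who leave, "data collected up to the time of withdrawal will be used" where applicable, and "Subjects who are withdrawn for any reason from the study after intervention will not be replaced".

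The primary endpoint (8.1) is the change in KOOS "scores at Week 52 post-operative compared to baseline". Section 12.6.1 states: "The Intent-to-Treat (ITT) population is defined as all randomized subjects". Section 12.7.5.1 states: "The primary analysis will be conducted on the Intent-to-treat (ITT) population". Major protocol violators are left out only of the per-protocol set (12.6.2), which is supportive (12.7.5.2). Section 12.3 plans for 82 randomised subjects and 70 completers: "The discontinuation rate is predicted to be no more than 15" per cent.

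**The concern.** The off-study rule and the primary analysis pull in opposite directions. The analysis needs a Week 52 KOOS from every randomised subject, adherent or not. The rule allows data collection to stop because a subject did not adhere, even if that subject still consents and could still answer the questionnaire. A statistical analysis plan can model the missing score, but it cannot supply a score that was never collected.

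The loss could also be related to outcome. Section 13.8.1 lists treatment failure from not complying with rehabilitation among the procedural risks, and compliance with the rehabilitation guideline is recorded at Day 10 and Week 6 (11.3.3, 11.3.4), long before Week 52. At stake are some precision in the Week 52 comparison and, if the rule were applied unequally between arms, some bias against a margin of 8 points.

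**Working it through.** **The wording.** Three readings of the non-adherence item in 10.3.2 are worth testing.

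1. *It restates withdrawn consent.* No. Consent is a separate item in the same list, and nothing ties non-adherence to it.
2. *It restates a ground in 10.3.1.* No. That section contains no such ground, so the two sections do not match.
3. *It means only subjects who stop giving follow-up.* Possible, but the text does not say so. Refusal appears only jointly with withdrawn consent, and loss to follow-up is described separately through failed contact attempts. A subject who can be reached, still consents and misses visits fits neither description. On this reading the item covers that subject, who might still give a Week 52 KOOS.

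On the literal reading, and on reading 3, the rule can therefore end scheduled KOOS collection in a subject whom the primary analysis includes.

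**The plan's own sample size.** Inputs from 12.3: 70 completers, 15% discontinuation, 82 randomised.
- 70 / 0.85 = 82.35, which reproduces the stated 82 to within one subject.
- 82 × 0.85 = 69.7, about the 70 required. The plan can lose 12 of 82 (14.6%), so there is almost no slack.

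**Precision (illustration).** Inputs from 12.3: 35 per arm, 80% power, margin 8, two-sided 0.05. The readable text gives no SD. Assuming a true difference of zero, the SD is back-solved:

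SD = √[35 × 8² / (2 × (1.960 + 0.842)²)] = 11.95.

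Power = Φ(8/SE − 1.960), with SE = SD × √(2/n):

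| Week 52 subjects per arm | SE | Power |
|---|---|---|
| 38 | 2.740 | 83.1% |
| 37 | 2.777 | 82.1% |
| 36 | 2.816 | 81.1% |
| 35 (plan) | 2.856 | 80.0% |
| 34 | 2.897 | 78.9% |
| 33 | 2.941 | 77.6% |
| 32 | 2.986 | 76.4% |

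Because the SD is assumed, a range is needed. Going from 35 to 33 per arm changes power from 91.7% to 90.1% at SD 10, from 60.7% to 58.2% at SD 15, and from 38.7% to 36.9% at SD 20. The level depends strongly on the SD. The cost of losing two per arm is about 1.6 to 2.5 percentage points throughout.

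**Bias (illustration).** Take one arm of 41 and remove one subject whose unseen Week 52 change is d points below the mean m of the other 40. The full mean is (40m + (m − d))/41 = m − d/41, and the observed mean is m. The shift is d/41 per excess subject:
- d = 5: 0.12 points (1.5% of the margin)
- d = 10: 0.24 points (3.0%)
- d = 20: 0.49 points (6.1%)

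The shift favours the arm that loses the subject, and it reverses if that subject would have done better than the rest. Equal losses with equal deficits in both arms cancel. The values of d are assumptions. The formula is for a simple observed mean; the planned repeated-measures analysis of covariance may recover part of the shift from earlier KOOS visits.

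**The case against.** The best defence is that 10.3.2 describes subjects who have already stopped, while 10.3.1 is where withdrawal is decided. Elsewhere non-adherence is something to record: the flowchart collects protocol deviations at every visit through Week 104, 13.3.5 sends them to a case report form, and 12.6.2 handles major violators in the per-protocol set. This makes the benign reading plausible. But none of these places says that a non-adherent subject stays in follow-up, and 10.3.2 says such a subject is off-study.

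It can also be said that the intervention is one operation on Day 0, with rehabilitation left to the investigator's standard of care, so little remains to adhere to except attending visits. This stands: the affected group may be very small.

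The retrieval sentence in 10.3.2 is not limited to adverse events, so a KOOS could be sought under it. It operates only after off-study status, however, stresses adverse events at discontinuation, and keeps nobody on the visit schedule. If off-study status counts as termination under 12.5.1, the subject would also be told the assignment, and a later KOOS would be unblinded self-report.

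Two stronger inferences fail. A reader might infer that the phrase is redundant and that deleting it settles the matter. It does not, because the reachable, consenting subject who misses visits would be left without a stated status. A reader might also infer that the rule underpowers the trial or favours one device. The protocol gives no non-adherence rate, no outcome deficit and no evidence of unequal use. Off-study subjects also remain in the intent-to-treat population, with their earlier data used where applicable.

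**Conclusion.** The point holds as a fault in a stated rule. Section 10.3.2 makes undefined non-adherence sufficient for off-study status, does not match 10.3.1, and can cost Week 52 KOOS data that the primary analysis calls for. This conclusion rests on the wording and needs no assumption.

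The consequence is of unknown and possibly small size. Within the 15% allowance, planned power is unchanged. Beyond it, each further subject lost per arm costs a little over one percentage point of power at the back-solved SD. Bias needs a loss that is both informative and different between arms; if rates and deficits are equal, only precision suffers. The change is worth making because it is cheap and the lost scores could not be recovered afterwards, not because harm to the result has been shown.

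**What to change.** In 10.3.2, remove non-adherence as a stand-alone off-study ground and state that non-adherence or missed visits alone do not end follow-up. Add that randomised subjects who have not withdrawn consent, have not been withdrawn under 10.3.1 and are not lost to follow-up remain in the study. This includes subjects who can be reached but miss visits. They are still approached for scheduled visits, with KOOS at Weeks 52 and 104. Non-adherence continues to be recorded as a protocol deviation (13.3.5) and handled through the supportive per-protocol analysis (12.6.2, 12.7.5.2), as the protocol already provides. Withdrawal under 10.3.1 is unchanged.

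The cost is a short amendment and some added follow-up effort, probably for few subjects, although the protocol gives no number. No new visit or procedure is needed.

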### **10.3.3 Study Site Termination**

A specific study site in this multi-center study may also warrant termination under the following conditions:

- Failure of the Investigator to enroll subjects into the study at an acceptable rate;
- Failure of the Investigator to comply with ICH guidelines, IRB/REB policies and procedures and/or regulatory body(s) regulations;
- Knowingly submitting false information from the study site to the Sponsor or its designee, IRB/REB, and/or regulatory body(s), as applicable; or
- Insufficient adherence to protocol requirements.

## **10.4 Prior and Concomitant Therapy**

Information on concomitant medications will be recorded on the Concomitant Medication CRF. Any medication used by the subject will be considered concomitant medication (e.g.,

aspirin, Tylenol, vitamins, dietary supplements, etc). Any changes in medication must be noted on the Concomitant Medication CRF.

Any other investigational drug or approved therapy for investigational use is not permitted during study participation.

## **11. STUDY PROCEDURES**

### **11.1 Study Interventions**

#### **11.1.1 Single Medial Femoral Chondral Lesion Treatment plus Partial Medial Meniscectomy Procedure**

A diagnostic arthroscopic evaluation will be conducted to confirm the area of treatment. If all arthroscopic eligibility criteria are met, the subject will be randomized to one of the following two treatments:

- Radiofrequency-Based Debridement (study devices)
- Mechanical Debridement (control device)

If randomized to Radiofrequency-Based Debridement, the subject will receive the Quantum 2 Controller plus Paragon T2 ICW Wand or the WEREWOLF Controller plus FLOW 50 Wand.

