### **Intra-operative Exclusion Criteria**

Subjects will be excluded from the study, if they meet ANY one (1) of the following criteria:

1. Has more than 1 chondral lesion requiring treatment
2. Requires concomitant procedures (i.e., anterior cruciate ligament repair, high tibial osteotomy), excluding partial medial meniscectomy
3. Has a medial meniscal tear not requiring treatment
4. Has a medial meniscal tear requiring a procedure other than partial meniscectomy
5. Has a lateral meniscal tear requiring treatment

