### **11.3.2 Visit 2: Surgery (Day 0)**

If the Investigator(s) discovers the presence of a condition at the time of surgery that would render the subject ineligible for study participation, the subject should be considered as an intra-operative failure and be discontinued from the study. The subject should receive the standard of care as determined by the Investigator(s).

The primary reason for termination or discontinuation will be documented on the End of Study CRF.

If the subject continues to meet eligibility, the data collected will include, but not be limited to:

- Subject randomization
- Date and time of surgery
- Device information
- Tourniquet time
- Duration of surgery (start and stop hh:mm from the first incision to the final closure)
- Anesthesia type and time of administration
- Adverse Events, if applicable
- Concomitant medication, if applicable

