**and**

- a medial meniscus tear requiring partial meniscectomy

- **End of Study**

- Subjects will not be randomized and be considered off study if they meet **any one (1)** of the following intra-operative exclusion criteria:

- Has more than 1 chondral lesion requiring treatment
- Requires concomitant procedures (i.e., anterior cruciate ligament repair, high tibial osteotomy), excluding partial medial meniscectomy
- Has a medial meniscal tear not requiring treatment
- Has a medial meniscal tear requiring a procedure other than partial meniscectomy
- Has a lateral meniscal tear requiring treatment

- Subjects will not be randomized and be considered off study if they **do not** meet **any one (1)** of the following intra-operative inclusion criteria:

1. Arthroscopic confirmation of a lesion requiring treatment meeting the following parameters:
  - a. Single, treatable chondral lesion, localized to the medial femoral condyle,
  - b. ICRS Grade 2 with widely displaceable fibrillation or flaps or Grade 3A,

c.  $< 4\text{cm}^2$  in size

- An End of Study Case Report Form (CRF) will be completed

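### Nothing requires the partial meniscectomy to come before allocation is disclosed, so an unmasked surgeon may perform it knowing the arm; the intra-operative failure rule also lacks an explicit cut-off at randomisation.

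*Protocol*

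**What the plan says.** Protocol 11.1.1 opens with the diagnostic step: "A diagnostic arthroscopic evaluation will be conducted to confirm the area of treatment". Randomisation is the next event described: "If all arthroscopic eligibility criteria are met, the subject will be randomized to one of the following two treatments". Section 11.3.2.1 lists what must hold at that moment. Besides the chondral lesion criteria, it requires "a medial meniscus tear requiring partial meniscectomy".

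For subjects who fail an intra-operative criterion, 11.3.2.1 says "Subjects will not be randomized and be considered off study if they meet" any exclusion on its list. One of these is "Has a medial meniscal tear requiring a procedure other than partial meniscectomy", which also appears in the intra-operative exclusion criteria of 10.2. Section 11.3.2 deals with a disqualifying condition discovered at the time of surgery: "the subject should be considered as an intra-operative failure and be discontinued from the study". The next part of 11.3.2 begins "If the subject continues to meet eligibility, the data collected will include, but not be limited to", and randomisation is the first item listed there.

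Section 12.5 describes masking of subjects (12.5.1) and of the MRI readers (12.5.2). Section 12.6.1 states: "The Intent-to-Treat (ITT) population is defined as all randomized subjects".

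**The concern.** The trial compares two ways of debriding the chondral lesion, but each randomised subject also has a partial medial meniscectomy in the same operation. KOOS cannot separate the effects of the two procedures. The operating surgeon has to handle the assigned device and so cannot be masked to the chondral step. The meniscectomy could be shielded from that knowledge in many cases, simply by keeping the allocation closed until it is done. The protocol does not ask for this. A surgeon who knows the arm could, without intending to, resect more or less meniscus in one group. A systematic difference of that kind would be counted as an effect of the debridement method, and no later analysis could reliably remove it.

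A smaller matter arises at the same point. The rule in 11.3.2 speaks of the time of surgery in general, and surgery continues after randomisation. The protocol does not say how to handle a randomised subject in whom a disqualifying finding emerges later in the operation.

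**Working it through.** **Sequence.**

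1. 11.1.1: diagnostic arthroscopy, then eligibility, then randomisation. No step stands between them.
2. 11.3.2.1: at randomisation the tear is described as requiring resection, which implies that the resection is still ahead. This is an inference from the wording; no section states the order of randomisation, meniscectomy and chondral treatment.
3. No section requires the meniscectomy to precede disclosure of the arm.
4. 12.5.1 and 12.5.2: subjects and MRI readers are masked. Nothing masks the operator.

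It follows that a surgeon who complies fully with the protocol may perform the meniscectomy knowing the arm.

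**Late ineligibility.** 11.3.2.1 keeps subjects who meet an intra-operative exclusion from being randomised. 11.3.2 places the intra-operative failure rule ahead of randomisation. Together they make it a pre-randomisation rule. What is missing is an explicit cut-off and an instruction for a finding made after allocation.

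**Illustration of size.** The inputs from Protocol 12.3 are a margin of 8 points, 35 completers per arm, 80% power and alpha 0.05 two-sided. The readable text gives no SD (Figure 12-1 is not shown), so the SD is assumed by solving the plan's own sample size backwards, with a true difference of 0 and the normal approximation:

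SD = 8 × √(35/2) / (z₁₋α + 0.842)

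- One-sided 0.025: 8 × 4.183 / (1.960 + 0.842) = 11.95; standard error of the difference SE = 11.95 × √(2/35) = 2.86.
- One-sided 0.05 (shown only to give a range): 8 × 4.183 / (1.645 + 0.842) = 13.46; SE = 3.22.

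The plan's 80% is reproduced by construction: Φ(8/2.86 − 1.960) = Φ(0.84) = 80%, and likewise Φ(8/3.22 − 1.645) = 80%.

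Now let the meniscal step shift the group difference by 1 point, which is 1/8 = 12.5% of the margin.

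| Direction of shift | One-sided 0.025, SD 11.95 | One-sided 0.05, SD 13.46 |
|---|---|---|
| Against radiofrequency: power, Φ(7/SE − z) | Φ(2.451 − 1.960) = 69% (from 80%) | Φ(2.176 − 1.645) = 70% (from 80%) |
| Favouring radiofrequency, true difference at the margin: false non-inferiority, Φ(−z + 1/SE) | Φ(−1.960 + 0.350) = 5.4% (from 2.5%) | Φ(−1.645 + 0.311) = 9.1% (from 5%) |

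The documents give no evidence on the actual size of such a shift; 1 point is a unit for scale.

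**The case against.** The strongest objection is that the sequence is inferred. A tear that requires partial meniscectomy is an eligibility description and does not fix operative order. This stands. A reader might infer that all 82 subjects have the meniscectomy after allocation, but the documents do not support so flat a statement. They support only that nothing prevents it and that the text points that way.

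A reader might also infer that subjects found ineligible during the meniscectomy are discontinued after randomisation, in conflict with the ITT definition. The documents do not say so. Section 11.3.2.1 withholds randomisation from subjects who meet an exclusion, the meniscal ones included, and 11.3.2 puts the failure rule before randomisation. Leaving the study does not remove a subject from ITT either, and 10.3.1 keeps data collected up to withdrawal for analysis where applicable. What remains is an unwritten case, not a contradiction.

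Three further points deserve weight. Subjects are masked and KOOS is self-reported, which protects the reporting of the outcome; it does not protect the way the meniscectomy is carried out. The surgery data list in 11.3.2 names no extent of resection, but it is expressly not exhaustive, so the case report form may capture it. Finally, nothing in the documents shows that surgeons would alter the meniscectomy if they knew the arm. The case for change therefore rests on cheap prevention and not on demonstrated bias.

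**Conclusion.** The point holds in a limited form. The protocol allows allocation to be disclosed before a co-intervention that belongs to every randomised subject's operation and is performed by an unmasked surgeon, although later disclosure would often be feasible. The resulting bias could run either way and its size is unknown. Under the back-solved SDs, a true difference of 0 for power and a hypothetical 1-point shift, power falls by about 10 to 11 percentage points if the shift runs against radiofrequency. If it favours radiofrequency, the false non-inferiority rate about doubles, from 2.5% to 5.4% at one-sided 0.025. The second direction matters more for a non-inferiority claim.

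On late ineligibility, the finding is a missing cut-off at randomisation and nothing stronger. Both parts concern trial conduct, so an analysis plan could not make them good afterwards. This is a low-cost improvement and not a flaw that invalidates the design.

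**What to change.** In 11.1.1 and 11.3.2.1, state that the allocation is disclosed as late as the surgeon's usual operative sequence allows and only after all intra-operative criteria are confirmed. Where the meniscectomy is done first, disclosure follows its completion and comes immediately before the chondral lesion is treated. The text should set the moment of disclosure and leave the surgical order to the surgeon.

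In 11.3.2, state that discontinuation as an intra-operative failure applies only before randomisation, in line with 11.3.2.1. Add that a subject found ineligible after randomisation stays in follow-up and in the ITT analysis.

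The cost is amendment wording and a small adjustment to theatre workflow. The protection is partial: for surgeons who treat the lesion first, the meniscectomy is still done with the arm known, and the chondral step remains unmasked for everyone.
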